#### EXPECTED RESULTS

---

The off- oxygen consumption and HHb kinetics will be determined using a mono-exponential model which incorporates an amplitude, time constant and time delay. As the recovery of muscle and total body oxygenation from both maximal and submaximal exercise is delayed in sedentary participants, it is expected that the exercise training, in particular the periodized training group, induces a decrease of the time constant of the exponential decrease of these parameters.

#### 4. BODY COMPOSITION - DUAL ENERGY RADIOGRAPHIC ABSORPTIOMETRY (DXA)

All the patients will be tested in the morning with a 12-h fasted no caffeine and alcohol, refrained from the moderate to vigorous exercise at least 24-h. Total and regional body mass (bone mineral content, lean soft-tissue and fat mass) is estimated using dual energy radiographic absorptiometry (DXA) (Hologic Explorer-W, fan-beam densitometer, software QDR for windows version 12.4, Hologic, USA). The attenuation of x-rays pulsed between 70 and 140 KV synchronously with the line frequency for each pixel of the scanned image. The same lab technician will perform the scans, and execute the analyses according to the standard analysis protocol. Total body skeletal muscle mass (TBSMM) will be calculated as  $TBSMM = (1.13 ALST) - (0.02 \text{ age}) + (0.61 \text{ sex}) + 0.97$ , where ALST means appendicular lean soft tissue. Skeletal muscle mass (kg) will be normalized by height (kg/m^2) and termed skeletal muscle index to verify the level of physical disability risk. Height will be measured to the nearest 0.5 cm with a stadiometer (SECA, Hamburg, Germany), body weight (SECA, Hamburg, Germany) and body mass index (BMI) (kg/m^2) will be calculate for height and body weight from the DXA. Body circumferences at the waist will also be measured using an inelastic flexible metallic tape (Lufkin W606PM, Vancouver, Canada), to the nearest 0.1cm. All anthropometric procedures will be led by the same certified technician.

#### EXPECTED RESULTS

---

DXA provides descriptive data on the body composition of all patients from the studied groups and will be important to monitor the changes in body composition over time and to quantify the intervention effects particularly regarding fat free mass and muscle wasting. It will also allow adjustments to the expected differences between groups at the end of the study. It is not probable to find exercise-related changes in body weight but small reductions in percent total body and regional fat are desirable, as well as increases in lean soft tissue of the lower limbs in the exercise groups. The variables obtained in this task are primary endpoints of purpose 1 and secondary endpoints of purpose 2. We expect small reductions in regional fat layer thickness in the exercise groups, especially in periodized training group.

#### 5. OBJECTIVE MEASURED PHYSICAL ACTIVITY

Each participant will use the ActiGraph GT3X+ and given oral and written instructions on how to wear the accelerometers for the following 7 days. The ActiGraph GT3X+ (AG; ActiGraph, Pensacola, FL) is able to assess acceleration in the vertical, antero-posterior and medio-lateral axes. It is a reliable instrument with high inter-instrument reliability and intra-instrument reliability within frequencies that are common in human activities. This device has been widely used in research, with good validity for measuring physical activity levels. The

ActiGraph GT3X+ will be attached to an elastic waist belt and placed in line with the axillary line of the right iliac crest. Participants will be asked to wear the accelerometer from the moment they wake up until they go to bed at night, and requested to remove it only during water-based activities such as showering and swimming and when they go to bed. ActiGraph GT3X+ will be initialized using a sample rate of 30 Hz and then downloaded using the low filter extension option in Actilife5 Software v5.7.4 (ActiGraph, Pensacola, FL). The cut off points previously used in an older sample of adults to calculate daily times in each activity intensity band will be: sedentary (<1.5 MET) 0–199 counts per minute (cpm); light (1.5–3 MET) 200–1998 cpm; moderate to vigorous physical activity (>3 MET):  $\geq 1999$  cpm. Sensitivity analyses will also be performed using a more conservative cut point of zero cpm to differentiate sedentary time from activity. All physical activity variables will be converted to time (in minutes) per valid day.

## EXPECTED RESULTS

---

This assessment will be used as a control of the physical activity or inactivity of the participants. The ones who reported at least moderate-intensity cardiorespiratory exercise training for  $\geq 30$  minutes per day on  $\geq 5$  days a week for a total of  $\geq 150$  minutes per week, vigorous-intensity cardiorespiratory exercise training for  $\geq 20$  minutes per day on  $\geq 3$  days a week ( $\geq 75$  minutes per week), or a combination of moderate and vigorous intensity exercise to achieve a total energy expenditure of  $\geq 500$ -1000 MET minutes per week, consistent with the recommendations of the American College of Sports Medicine, will be classified as active. Those not meeting this criterion will be considered inactive. We expect increases in time spent in moderate-to-vigorous physical activity from M0 to M3 in both exercise groups.

---

## 6. FUNCTIONAL PHYSICAL FITNESS TESTS

The functional physical fitness tests are a simple, reproducible, readily available tool frequently employed to assess submaximal functional capacity and evaluate the response to intervention. The six minute walking test (6MWT) will be performed indoors, along a long flat, straight, enclosed 20-meter corridor with a hard surface that is seldom. Patients will be instructed to walk at their own pace according to their tolerance to exercise for 6 minutes, with rest stops as needed. The final result will be the distance in meters covered in the 6 minutes. Total distance during the test will be recorded. Because the body weight of patients directly affect the energy and work required to walk, it will be used the body weight-walking distance (body weight  $\times$  walking distance) to assess the walking capacity of subjects. The aim of the 6MWT is to assess aerobic endurance. The 30-second chair stand, assesses the lower body strength, needed for numerous tasks such as climbing stairs or walking. Patients will be instructed to sit and stand as faster as they can in 30 seconds with arms folded across chest. The 8-foot (2.44 meters) up and go test evaluates the agility/dynamic balance, which is important in tasks that require quick maneuvering. It will be evaluated the time in seconds that the participant needed to get up, walk the distance of 2.44 meters and return to the initial position. For the flexibility, it will be assessed in both upper and lower body. The chair sit-and-reach aim to assess the lower body flexibility from a sitting position at front of a chair with the leg extended and hands reaching toward the toes, the number of cm between extended fingers and tip toes (+ or -) will be measured. To assess the upper body (shoulder) flexibility, it will be used the back scratch test with one hand reaching over the shoulder and one up the middle of the back, it will be taken the number of cm between extended middle fingers (+ or -).

## EXPECTED RESULTS

---

The variables measured in this task are primary end-points of purpose 1. We expect gradual improvements of the functional fitness test scores from M0 to M3 in both exercise groups, in particular the periodized training group.

---

### 7. ISOMETRIC STRENGTH

Handgrip strength will be assessed by a portable hand dynamometer JAMAR plus digital (Sammons Preston, Bolingbrook, IL). Subjects will be assessed on both hands alternately. Handgrip assessment will be conducted with the patients in a seated comfortable position, with the shoulder adducted and close to, but not supported by, the trunk. The elbow of the assessed limb should be flexed to 90 degrees and the forearm should be in a neutral position (halfway between supine and pronation position). A variation of 0-30 degrees in the wrist extension will be allowed. Each subject will be assessed in three attempts for both hands alternately. In each attempt the subject will exert the maximal grip strength on the hand dynamometer with the assessed limb during 5 seconds. After each attempt, there will be a resting period of 60 seconds that will be used both for recovery and for changing the handgrip dynamometer to the opposite hand. All patients will be instructed not to perform a Valsalva manoeuvre during the tests.

## EXPECTED RESULTS

---

The variables measured in this task are secondary aims of the project. It remains to be determined whether a training protocol that specifically focuses on increasing hand grip strength would have a greater impact on overall functional status. Maximal isometric strength is not expected to decrease in both exercise groups.

---

### 8. MAXIMAL STRENGTH

Maximal strength will be assessed by 1RM test for each of six weight exercises on variable resistance machines (Life Fitness) available at the EUL as follows, leg press, leg extension, leg curl, low row, chest press and lat pull down. The protocol test of 1RM was determined as previously described in our prior studies. The protocol will include four pre-test sessions to familiarize each patient with the test procedures. Correct exercise and breathing techniques (avoidance of the Valsalva manoeuvre) will be practiced. Prior to the 1RM determination, each subject warmed-up for 15 min on a treadmill at 50% of HRR and then performed ten stretching exercises. To warm-up before using a machine, each patient will be asked to perform eight repetitions using a relatively light resistance, followed by a 30 second rest. A second set of four repetitions using a moderate resistance will be then used, followed by a 1 minute rest. After that each patient will be asked to perform single repetitions until the 1RM was reached. The rests between attempts will be 1–2 min. The resistance will be increased by approximately 5 kg, or by 2.5 kg when the subject was near his maximum. Strength will be recorded as the maximal number of kilograms lifted in one full range of motion. The order of the tests will be the same for all patients, and these exercises will be the same as those used for the ET.

## EXPECTED RESULTS

---

The variables measured in this task are primary endpoints of aim 1. Significant improvements in maximal strength are possible as high from 50 and 69% of 1-RM among middle-aged CAD participants and over 80% of 1- RM in elderly CAD participants.

---

## 9. QUALITY OF LIFE QUESTIONNAIRE

The Short Form-36 Health Survey (SF-36) is a self-assessment health status questionnaire composed of 36 questions about socio-demographic, health and personal behavior. It was designed for use in clinical practice and research, health policy evaluations and general population surveys. The 36 questions in the SF-36 survey capture the subject's perception of their general health by sorting them into multi-item scales that assess 8 concepts. The 8 subscales are as follows: physical functioning (10 questions); role/physical (4 questions); bodily pain (2 questions); general health (10 questions); vitality/energy (4 questions); social functioning (2 questions); role/emotional (3 questions); mental health/emotional wellbeing (5 questions). The SF-36 also provides 2 important summery measures of health-related quality of life: physical component summary and mental component summary scales. The strength of both scales lies in their ability to distinguish a physical from a mental outcome. The items and dimensions in SF-36 were constructed using the likert method of summated ratings. This questionnaire has been used in CR programs. A Portuguese validated version of SF-36 is available.

---

## EXPECTED RESULTS

The variables measured in this task are primary endpoints of aim 1 of the project, it is expected improvements in the quality of life for both exercise training groups and a bi-directional relationship with increased physical activity and vocational status.

---

## 10. EXERCISE TRAINING PROGRAM

The ET program will be carried out mostly in groups at the EUL gymnasium, 3 times a week (60 minutes per session) on non-consecutive days for 48 weeks and supervised for both groups. To ensure that total training loads (i.e., volume x intensity) were similar in both groups despite differences in intensity, it will be used the training impulses (TRIMP) method from Edwards for the aerobic component and the volume load method for the RT component. All sessions will include 10 minutes of warm up and cool down standardized for both groups. The warm up will focus on pulse raising, mobility and preparatory stretching for the conditioning component. Cool down will include transition from conditioning component to the stretching phase, which comprises static and dynamic stretching exercises for all major muscle groups. In every 10 exercise sessions, it will be prescribed multifunctional exercise with the aim to develop other fitness components such as agility, flexibility and balance. In total, approximately 14 multifunctional exercise sessions will be prescribed during 48 weeks. Sessions will be deemed completed when at least 90% of the prescribed exercises have been successfully performed.

**Periodized group:** the exercise prescription will be gradually progressed through various combinations of duration, frequency and/or intensity of training. Over the first 15 exercise sessions, it will be prescribed continuous ET: 20 minutes on an ergometer with the intensity of the first AT (AT1) measured on the CPET or 50-60% of the HRR, if the AT could not be adequately determined, Borg Rating of Perceived Exertion (RPE) equivalent 9-11; and anatomical RT adaptation (2 sets of 15-20 repetitions 50% 1RM); from the 16th session until the 30th session, it will be prescribed combined ET with HIIT: 4 interval training periods of 2 minutes (AT2 intensity or 80-90% HRR, if AT2 could not be determined, RPE 15-17) and 4 active pauses of 2 minutes (below AT1 or 40-50% HRR, RPE 6-9) between interval training periods; and hypertrophy (2 sets 8-12 repetitions at 60% 1RM). From the 31st until the 45th exercise session, after the adjustments of the respectively time point assessments, it will be done 20 minutes of MCT with the intensity between AT1 and

AT2 or of 60-70% HRR, RPE 12-13 and maximal strength (2 sets of 6-8 repetitions at 80% 1RM). From the 46th until the 60th exercise sessions, it will appear again the HIIT with the same pause intensities but different work intensities (above AT2 intensity or > 90% HRR, RPE 17-19 and active pauses at AT1 or 50-60% HRR, RPE 9-11) with hypertrophy (2 sets 8-12 repetitions 60% 1RM). At the end of the 60th session, the same exercise prescription will start over again, MCT with maximal strength, HIIT with hypertrophy, MCT with maximal strength and HIIT with hypertrophy until the 134th session. The 2 types of RT prescribed will focus on the major trunk, upper and lower body muscle groups in circuit weight training and/or machines (Life Fitness, Rosemont, IL, USA). The patients will be instructed about the correct exercise techniques and to avoid the Valsalva maneuver.

**Non periodized group:** in accordance with the ACSM Guidelines 2014 for CVD, participants will do a combined ET regime (aerobic and RT). Aerobic component: combine moderate (40% HRR) to vigorous (75% HRR) exercises 3 d.wk on nonconsecutive days, for 20 min per session, involving major muscle groups using the available ergometers (treadmill, indoor row and cycle ergometer) to perform continuous and rhythmic activities in nature. Resistance component: RT should be performed after the aerobic component of the exercise session to allow for adequate warm-up. Initial load should be trained initially with one set of 10–15 repetitions that can be lifted without straining (~30%–40% 1RM for the upper body; ~50%–60% 1 RM for the lower body). Low-risk patients may progress to 2–4 sets with 8–12 repetitions with a resistance of ~60%–80% 1RM with a rest interval of 2–3 min between sets. Each major muscle group (*i.e.*, chest, shoulders, arms, abdomen, back, hips, and legs) should be trained initially with one set; multiple set regimens may be introduced later as tolerated. Perform 8–10 exercises of the major muscle groups.

By design, the non periodized group involves an identical total training volume and time commitment but differed regarding metabolic stress induced by the periodized group. All patients will be monitored with a HR monitor (H7 Polar, Electro, Kempele, Finland) during the execution of the exercise session in order to achieve the HR training. Blood pressure will be assessed before and after completing each session. If necessary, the blood pressure will be measured during the ET session.

---

## 11. TRIMP CALCULATIONS

The quantification of the training load in the aerobic component by the Edwards method will be performed from the division of intensity zones related to maximal HR (HRmax) - Zone 1: 50 at 60% of HRmax; Zone 2: 60 at 70% of HRmax; Zone 3: 70 at 80% of HRmax; Zone 4: 80 at 90% of HRmax; Zone 5: 90 at 100% of HRmax. Since the HR prescription that are being used is in % HRR, it will be converted % HRmax to % HRR as it is possible to observe in *Table 1*. For estimation of the Edwards method, the time accumulated in each zone was multiplied by its value and the results obtained will be summed (*Table 2*).

Table 1: Methods of Estimating Intensity of Cardiorespiratory Exercise (Adapted from Garber et al)

Intensity	%HRR or %VO 2 R	%HR max	Edwards method Zone
Very light	< 30	< 57	1
Light	30 - < 40	57 - < 64	2
Moderate	40 - < 60	64 - < 76	3
Vigorous	60 - < 90	76 - < 96	4
Near maximal to maximal	≥ 90	≥ 96	5

HRmax, maximal heart rate; HRR, heart rate reserve; VO2R, oxygen uptake reserve.

Table 2: Intensity and duration, as quantified by daily trimp per every 15 exercise sessions during the training period for the periodized group and the non-periodized group.

		Aerobic Component													
		Linear Periodized Group										Non Periodized Group			
Number of sessions	total time	work sets	work (min)	rest sets	rest (min)	work (zone)	rest (zone)	extra (min)	extra (zone)	TRIMP daily	work sets	work (min)	work (zone)	TRIMP daily	
1 to 15	20	1	20	0	0	2	0	0	0	40	1	20	2	40	
16 to 30	20	4	2	4	2	4	2	4	1	60	1	20	3	60	
31 to 45	20	1	20	0	0	3	0	0	0	60	1	20	3	60	
46 to 60	20	4	2	4	2	5	3	4	1	60	1	20	3	60	
61 to 75	20	1	20	0	0	3	0	0	0	60	1	20	3	60	
76 to 90	20	4	2	4	2	4	2	4	1	60	1	20	3	60	
91 to 105	20	1	20	0	0	3	0	0	0	60	1	20	3	60	
106 to 120	20	4	2	4	2	5	3	4	1	60	1	20	3	60	
121 to 135	20	1	20	0	0	3	0	0	0	60	1	20	3	60	
										520					520

The equation for calculating the volume load for the RT is accomplished by multiplying the number of repetitions by the percentage of 1-RM. This equation is represented as the following: *Volume load (kg) = number of sets x number of repetitions x %1RM*. In both groups, TRIMP is similar (Periodized: 12820 vs Non Periodized: 12790).

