#### ***Symptom-limited exercise test***

A symptom-limited ramp incremental CPET, in accordance with the Clinician's Guide to Cardiopulmonary Exercise Testing in Adults, will be performed on a cycle ergometer (Ergostik, Geratherm Respiratory GmbH, Bad Kissingen, Germany) with breath-by-breath gas exchange measurements. Gas exchange analysis provides a highly reproducible measurement of exercise limitation and insights into the differentiation between cardiac or respiratory cause of dyspnea, assesses ventilator efficiency and carries prognostic information. After 2 minutes rest followed by 2 minutes unloaded pedaling and 2 more minutes at rest, each patient will be encouraged to exercise to exhaustion (20 Watt+20 Watt/min or 15 Watt+15Watt/min or 10 Watt+10 Watt/min), as defined by intolerance, leg fatigue or dyspnea unless clinical criteria for test termination occurred. Patients will continue seated on the cycle ergometer as soon as they stop, while recovery measurements are taken. Twelve-lead ECG will be recorded continuously and blood pressure will be recorded at baseline, every two minutes, at peak exercise and during recovery. Peak oxygen capacity will be considered the highest attained  $\text{VO}_2$  during the final 30s of exercise and ventilator AT will be estimate by the V-slope method. HR recovery as a simple marker of parasympathetic activity will be calculated as the difference between peak HR and HR one minute later. The recovery period will continue until 6 minutes after peak effort. Chronotropic response (CR) to exercise will be evaluated by the % of HR reserve (HRR) used at peak exercise.  $\text{CR} = [\text{peak HR} - \text{resting HR} / (220 - \text{age} - \text{resting HR}) \times 100]$ . A failure to use 80% of the HRR is defined as chronotropic incompetence. All patients should achieve a respiratory exchange ratio of  $>1.1$ , an indicator of

maximal effort in the CPET. The CPET will provide clinical information to patient screening and exercise intensity prescription.

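### The aerobic load match presumes %HRR prescription, but the periodized arm is prescribed from AT1/AT2, so equal load is not secured and the intensity basis differs by arm

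*Combined protocol and SAP*

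**What the plan says.** All references are to the combined protocol and SAP.

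- **Aim of the match.** Section 10 uses the Edwards training impulse (TRIMP) for the aerobic part: "To ensure that total training loads (i.e., volume x intensity) were similar in both groups". It then describes the result: "By design, the non periodized group involves an identical total training volume and time commitment".
- **Premise of the calculation.** Section 11 states, with no distinction between arms: "Since the HR prescription that are being used is in % HRR, it will be converted % HRmax to % HRR". Table 1 maps %HRR and %HRmax to Edwards zones 1 to 5. Table 2 gives each training component one fixed zone and totals 520 in each arm.
- **Periodized arm, sessions 1–15** (section 10): "intensity of the first AT (AT1) measured on the CPET or 50-60% of the HRR, if the AT could not be adequately determined".
- **Periodized arm, sessions 16–30, work intervals:** "AT2 intensity or 80-90% HRR, if AT2 could not be determined". The pauses are set below AT1, with 40–50% HRR as an alternative and no condition attached.
- **Periodized arm, from session 31.** Continuous blocks lie between AT1 and AT2, or at 60–70% HRR. The next interval blocks are above AT2, or above 90% HRR, with pauses at AT1 or 50–60% HRR. A bare *or* joins threshold and %HRR each time.
- **Comparator** (section 10): "combine moderate (40% HRR) to vigorous (75% HRR) exercises". No threshold is mentioned.
- **Source of the thresholds.** The symptom-limited test in section 2 describes one threshold: "ventilator AT will be estimate by the V-slope method". No method for AT2 appears.

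**The concern.** The load calculation describes a prescription that the periodized arm does not, in the first instance, receive. Two consequences follow.

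First, the planned load of a patient trained by threshold cannot be read from Table 1. The zone depends on that patient's heart rate at AT1 and AT2, which the documents do not give. Table 2's fixed zones are therefore an assumption about these patients, and the statement of identical volume rests on it.

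Second, the arms differ in more than periodization. The Background defines periodization as planned variation in intensity, volume and specificity. Setting intensity from gas-exchange thresholds is a separate feature, and only one arm has it. A between-arm difference in peak VO2, AT or VO2 kinetics could partly reflect how intensity was set. Because AT2 has no stated method and the later blocks have no rule for choosing between threshold and %HRR, the basis may also vary between periodized patients and over time.

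**Working it through.** **1. Reproduce the plan's figure.** Edwards TRIMP is the sum of minutes × zone. Table 2 has nine 15-session rows: one initial continuous row, four later continuous rows and four interval rows.

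- Periodized, Table 2's zones: 20×2 = 40 for the first row; 20×3 = 60 for each later continuous row; 8×4 + 8×2 + 4×1 = 52 for sessions 16–30 and 76–90; 8×5 + 8×3 + 4×1 = 68 for sessions 46–60 and 106–120.
- Total: 40 + 4×60 + 2×52 + 2×68 = 520.
- Comparator: 40 + 8×60 = 520.

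The totals agree with Table 2. All four interval rows print 60 rather than 52 or 68, but these differences cancel.

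**2. Read the %HRR bands through Table 1.** There, 40 to <60% HRR is zone 3, 60 to <90% is zone 4 and ≥90% is zone 5.

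| Periodized component | %HRR band | Zone by Table 1 | Zone in Table 2 |
|---|---|---|---|
| Sessions 1–15 | 50–60 | 3 | 2 |
| Pauses, sessions 16–30 | 40–50 | 3 | 2 |
| Continuous, from session 31 | 60–70 | 4 | 3 |

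The other components keep their zones, and a band's upper end-point is taken with the band. Total: 60 + 2×60 + 4×80 + 2×68 = 636, which is 636/520 − 1 = 22% above 520. So Table 2 does not follow from the %HRR bands either.

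The comparator's 40–75% HRR spans zones 3 and 4. Its total would lie between 9×60 = 540 and 9×80 = 720.

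**3. Read the thresholds.** Table 1 has no entry, so assumptions are needed. I assume:

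- AT1 falls in zone 2, 3 or 4, and pauses below AT1 are one zone lower;
- work at AT2 is in zone 4 or 5, and work above AT2 is in zone 5;
- continuous training between the thresholds is in zone 3 or 4, never below AT1's zone;
- the 4 extra minutes stay in zone 1.

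Lowest case (AT1 zone 2, AT2 work zone 4, continuous zone 3):
- first row 20×2 = 40;
- interval rows 8×4 + 8×1 + 4 = 44 and 8×5 + 8×2 + 4 = 60;
- total 40 + 2×44 + 4×60 + 2×60 = 488.

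Highest case (AT1 zone 4, AT2 work zone 5, continuous zone 4):
- first row 20×4 = 80;
- interval rows 8×5 + 8×3 + 4 = 68 and 8×5 + 8×4 + 4 = 76;
- total 80 + 2×68 + 4×80 + 2×76 = 688.

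Against 520 the range is −6% to +32%. Against 636 it is 488/636 − 1 = −23% to 688/636 − 1 = +8%. The sign is undetermined on either reference. Part of the excess over 520 is the Table 1/Table 2 mismatch in step 2, not the threshold basis.

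**The case against.** Four points can be made for the plan.

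- **The arms are matched as planned.** This stands: 520 against 520 reproduces. A reader might infer that the planned loads are unequal, but the documents do not show that. What they leave open is whether equality holds for patients trained by threshold.
- **Each threshold is paired with a %HRR band, so the premise is roughly right.** This stands in part. On the plan's pairing (AT1 at 50–60%, AT2 at 80–90% HRR), the narrow AT1–AT2 window of 60–80% HRR lies wholly in zone 4, as does the paired 60–70% band. A reader might take a one-zone rise in the 60 continuous sessions after session 30 (20×60 = 1200 TRIMP, or 15% of 15×520 = 7800) as the effect of threshold prescription. It is not. On this pairing, thresholds leave those sessions in the same zone or, if AT1 is nearer 50%, partly in a lower one. The upward step is the Table 1/Table 2 mismatch. But the pairing is a group-level stand-in and does not say where an individual's thresholds fall.
- **The comparison is of two regimes that differ in metabolic stress by design.** This is fair, and %HRR is itself scaled to the patient. But the stated purpose contrasts periodized with non-periodized training, and nothing in the documents makes the intensity basis part of that contrast.
- **Edwards TRIMP can be computed from heart rate whatever the prescription basis.** This is correct, and it is the way out. However, section 13 plans no between-arm comparison of delivered load. Section 11's closing totals (12820 against 12790) are planned values whose build-up is not shown.

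**Conclusion.** The point holds in a limited form. Section 11's premise conflicts with section 10 for the periodized arm, Table 1 cannot place a threshold in a zone, and AT2 has no stated method. The equality of aerobic load is therefore planned but not secured, and the intensity basis differs by arm in addition to periodization.

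The size of any imbalance is unknown. The range of 488 to 688 rests on the zone assumptions listed above and is not an estimate.

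Three stronger readings are not supported:

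- *Table 2 describes patients on the %HRR fallback.* Their bands give 636 through Table 1, not 520.
- *Every periodized session is threshold-based, with %HRR only as a fallback.* The fallback condition is explicit only for sessions 1–15 and the work intervals of sessions 16–30.
- *Most periodized patients will train by threshold.* No rate of threshold determination is given.

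**What to change.** 1. Reconcile the symptom-limited test in section 2 with sections 10 and 11 on the basis of intensity in each arm, on when %HRR replaces a threshold, and on how AT2 is determined. The choice is the sponsor's.
2. Replace the %HRR premise in section 11 with each patient's delivered Edwards TRIMP, computed in both arms from the session heart-rate monitor. State that the heart-rate data are stored; section 10 says only that patients are monitored. State which zone limits apply, since zone 3 is 70–80% HRmax in section 11's text but 64 to <76% in Table 1.
3. Add to section 13 a report of delivered TRIMP by arm and, within the periodized arm, by basis used (threshold or %HRR). The report by basis is descriptive.
4. Do not claim equal dose unless delivered load is shown to be similar. Say beforehand what difference would count as similar; a non-significant test in 50 patients would not show it.
5. If both bases remain, word the conclusion as a comparison of the two regimes, including how intensity was set.

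The cost is protocol wording, plus storing and processing heart-rate data from monitors that patients already wear. No further tests or patients are needed.
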